## **II. Background and Significance**

*Background* - Herpes zoster (HZ) is a frequently severe infection caused by varicella-zoster virus (VZV). 60% of the annual 1.2 million US cases occur in people  $\geq 50$  years of age, although immune compromise is another risk factor for HZ (1,2). Common to these two risk factors is a significant decline, to a critical level, of VZV T-cell mediated

immunity (VZV-CMI) initially stimulated by the primary VZV infection (childhood varicella) (3-5). Varicella also results in the lifelong persistence of VZV in sensory ganglia. Sporadic reactivation of VZV occurs, but such events typically remain subclinical because of VZV-CMI. However, when an adequate VZV-CMI response to reactivation is absent, propagation of VZV in the ganglion continues and spreads down the sensory nerve to cause the characteristic signs and pain of HZ (6). A live attenuated HZ vaccine (ZVL) has been available since 2006 to prevent this, but its efficacy for preventing HZ is 51% in the 1st 3y after immunizations and drops sharply after 5y, and efficacy decreases with the age of the vaccinee (7). Shingrix (RZV), a recombinant VZV glycoprotein E (gE) adjuvanted vaccine, which became available late in 2018, is remarkably superior, with 97% overall efficacy against HZ. RZV protection declines little over time (8). The efficacy of RZV is unique compared with any approved vaccines for older adults and any candidate vaccines for herpesviruses. The magnitude and persistence of RZV immunogenicity represent a paradigm shift in vaccinology that warrants granular studies.

**Significance** - Central to understanding the superiority of RZV is determining the timing, magnitude, and nature of the systemic and local immune events at the site of VZV reactivation and replication. *Since the milieu of sensory ganglia cannot be directly evaluated, this proposal will use intradermal (ID) administration of live attenuated VZV vaccine (vOka strain) to simulate reactivated VZV replication in the skin.*

Ageing is associated with increasing frailty and multiple concomitant medical conditions, which are compounded by an increasing incidence of infections as a consequence of immune senescence. The resulting societal burden is evident from increased hospitalization and medical costs among older people (9). This is clearly demonstrated by HZ, where the incidence, severity, hospitalization, and complications increase dramatically after the 6th decade of life (10). This problem will intensify in the future, since there are currently 110 million people in the US over 50y of age and there will be 32 million people  $\geq 80$ y in 2050 (11). Understanding how a vaccine for older people successfully limits a common infection (namely HZ) in ageing individuals may be applicable to the general problem of improving the immunogenicity of other vaccines for older people. Specifically, this proposal determines how a vaccine shapes the early immune response to a live attenuated vOka VZV challenge and limits VZV infection at the challenge site. Local intracellular vOka antigen production and DNAemia resulting from the challenge provide endpoints for this new model to understand the effect of early post-reactivation immune responses on VZV replication.

### **III. Preliminary Studies/Progress Report**

The following preliminary studies have been completed in support of this proposal:

1. We submitted the results of a 1 year study (so far in year 4 of a 5 year study) to *Nature Vaccine* that determined that RZV generates superior VZV-specific T cell memory responses compared to ZVL. All of the immunologic assays needed for the proposed trial have been validated and appear in our published reports (12).

2. We published methods and findings that demonstrated that VZV DNAemia after a vOka skin challenge correlates with the differentiation and magnitude of VZV-CMI responses (13).
3. We published on the methods, safety, and immunogenicity of ID vOka (14).

4. Experiments in preparation for this proposal that have been completed include:

- a. Measures of plasma biomarkers after different modes of administration of ZVL and RZV.
- b. Measures of selected T cell and antigen-presenting cell responses after ZVL and RZV.
- c. Discovery of CD4+ and CD8+ epitopes that will be used for tetramer synthesis for the advanced immunologic assessments proposed.
- d. Skin specimens have been studied at the Human Immune Monitoring Shared Resource at the Anschutz campus using the 7-color Vectra 3 instrument. This methodology will be used to study local responses to the ID vOka challenge. We were able to detect VZV and immune cell phenotypes on these skin biopsies.

## **IV. Research Methods**

### **A. Outcome Measures/Study Endpoints**

Primary Endpoint - Rate of VZV DNAemia after ID vOka challenge.

Secondary Endpoint – Duration and magnitude of VZV DNAemia and rate of VZV RNAemia. VZV- and gE-specific T cell and other immune cell responses in blood and at the site of ID vOka challenge; cytokines levels in blood and at the site of ID vOka inoculation; transcriptomics of immune cells in blood and skin biopsies; immunohistochemistry of skin biopsies of the ID vOka challenge.

Exploratory Endpoint –After RZV: Tetramer analysis of the T cell responses; T cell epigenome.

### **B. Description of Population to be Enrolled**

#### Inclusion Criteria

1. Subject able to understand and provide informed consent.
2. Age  $\geq$  50 years
3. Ambulatory and in generally good health except for common morbidities of older people;
4. Women of non-childbearing potential meet at least 1 of the following:
  - a. Achieved postmenopausal status, defined as cessation of regular menses for at least 12 consecutive months
  - b. Have undergone hysterectomy and/or bilateral oophorectomy
5. **Part A, Cohorts 1 and 2** – Documented evidence of immunization with ZVL (Cohort 1; n=35) or RZV (Cohort 2; n=35) at least 5 years previously;

6. **Part B, Cohorts 3 and 4** - HZ vaccine naïve - Cohort 3 (n=35) will be vaccinated with ZVL at study enrollment, **or** Cohort 4 (n=35) will be vaccinated with RZV at study enrollment.

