## **I. Hypotheses and Specific Aims**

### Hypotheses

- 1) Shingrix (RZV) recipients will have a lower rate of varicella-zoster virus (VZV) DNAemia after a live intradermal (ID) VZV challenge (vOka vaccine) than Zostavax (ZVL) recipients because of higher and/or more rapid VZV-specific T cell responses.
- 2) After a live VZV ID challenge, RZV recipients will have the same rate of VZV DNAemia whether the challenge was performed <1 or >5 years after vaccination; whereas ZVL recipients will have lower rates of VZV DNAemia if they are challenged <1 year after vaccinations compared with >5 years.
- 3) The peak memory VZV and/or gE Th1 responses to RZV mediate protective immune responses conferred by RZV against VZV DNAemia after VZV ID challenge; early responses may also play a role

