### Specific Aims/Study Objectives

**Primary Objective 1.** To compare the rate of vOka DNAemia within 7 days after ID vOka administration in adults who received RZV or ZVL >5y before the challenge.

**Primary Objective 2.** To compare the rate of vOka DNAemia after ID vOka challenge at <1y after RZV or ZVL vaccination and at >5y after vaccination.

**Secondary Objective 3.** To identify the characteristics of the immune responses to RZV that predict the immunologic control of vOka DNAemia after ID vOka challenge at <1y and at >5y after vaccination.

*Note:* This will include studies to further define epitope-specific immune responses, and will measure transcript profile and epigenetic changes in immune cells following vaccination.

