**Exclusion Criteria**

1. Inability or unwillingness of a participant to give written informed consent or to comply with study protocol.
2. Prior history of HZ;
3. Known history of hypersensitivity to ZVL or vaccine components in all study candidates and to hypersensitivity to RZV or vaccine components in Cohort 4.
4. Known neomycin contact allergy or other ZVL components such as gelatin.
5. Untreated anemia in Cohorts 1 and 2.
6. Blood products received in the 3 months prior to study enrollment or planned for the subsequent week for Part A; Part B requires the same exclusion but extends it to the week after the vOka challenge, which is 6 months after completing ZVL or RZV administration.
7. Any confirmed or suspected immunosuppressive or immunodeficient condition resulting from disease (e.g., malignancy, HIV), or immunosuppressive/cytotoxic therapy.
8. Use, or anticipated use, of immunosuppressants or other immune-modifying drugs during the period starting 30 days prior to ID ZVL challenge through 7 days after. This includes chronic administration of corticosteroids (>14 consecutive days of prednisone at a dose of  $\geq$  20 mg/day [or equivalent], long-acting immune-modifying agents, or immunosuppressive/cytotoxic therapy (e.g., medications used during cancer chemotherapy or to treat autoimmune disorders). *Topical, ophthalmic, intra-articular, or inhaled/nebulized steroids are allowed.*
9. Concomitant vaccine received within 2 (inactive) or 4 (live) weeks prior to the study for subjects in all Cohorts, and during the first week of the study. For subjects in Cohorts 3 and 4, no concomitant vaccine received within 2 (inactive) or 4 (live) weeks prior to ID vOka and for the following 7 days.
10. Women of child-bearing potential.
11. Pregnancy or breast-feeding.
12. Participation in a concurrent clinical study in which the subject will be exposed to an investigational product (drug or vaccine) during the period starting 7 days before the first dose of study vaccine through the completion of the study.
13. Antivirals with activity against VZV, including acyclovir, valacyclovir, ganciclovir, valganciclovir, foscarnet, cidofovir, brincidofovir and penciclovir within 7 days of the ID ZVL challenge.

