### **Schedule of Events – Cohort 3**

Cohort 3 – No Previous HZ Vaccine (to be admin ZVL)	Visit 1	Visit 2	Visit 3	Visit 4	Phone	Visit 5	Visit 6	Visit 7	Visit 8	Visit 9	Phone	Visit 10	Visit 11
	Day 0	Day 1	Day 3	Day 7	Day 9 (+3)	Day 30 (+7)	Day 150 (+44)	Day 151	Day 153 (+2)	Day 157 (+10)	+48 hours	60 Days after V6 (+30)	60 days after V10 (+30)
Informed consent, review of eligibility criteria	●												
Medical history and current medications	●						●						
Blood draw (60ml)	●	●	●	●		●	●	●	●	●			
Pre-vaccination body temperature	●						●						
Vaccination – Zostavax	●												
Vaccination (ID vOka challenge)							●						
AE assessment	●	●	●	●	●	●	●	●	●	●			
Vaccination – Dose 1 RZV 											● 		
Vaccination – Dose 2 RZV 												● 	

If subject wishes to receive RZV

**Cohort 4** (n=35) subjects will be enrolled, have blood (60ml) drawn, and will be administered RZV (2 doses –D0, D60) prepared and administered in accordance with the package insert, in the clinic. Participation will consist of 10 visits over the course of approximately 9 months. Blood will be drawn at Day 0, Days 61, 63, 67, and 90. These subjects will receive the challenge dose of vOka 6 months later at Day 240, with blood drawn, then drawn again at Days 241, 243, 247. Participation will consist of 10 visits over the course of approximately 8.5 months.

### Schedule of Events – Cohort 4

Cohort 4 – No Previous HZ Vaccine (to be admin RZV)	Visit 1	Phone	Visit 2	Visit 3	Visit 4	Visit 5	Visit 6	Visit 7	Visit 8	Visit 9	Visit 10	Phone
	Day 0	Day 7 (+3)	Day 60 (+14)	Day 61	Day 63	Day 67 (+3)	Day 90 (+7)	Day 240 (+14)	Day 241	Day 243	Day 247 (+3)	+48 hours after V 5, 6, 10
Informed consent, review of eligibility criteria	●											
Medical history and current medications	●		●					●				
Blood draw (60ml)	●		●	●	●	●	●	●	●	●	●	
Pre-vaccination body temperature	●		●					●				
Vaccination – Dose 1 RZV	●											
Vaccination – Dose 2 RZV			●									
Vaccination (ID vOka challenge)								●				
AE assessment	●	●	●	●	●	●	●	●	●	●	●	

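### Part B states no random allocation to ZVL or RZV and does not pre-specify pre-vaccination VZV immunity as a covariate, so the vaccine contrast at <1y is avoidably open to confounding

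*Combined protocol and SAP*

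**What the plan says.** **Allocation.** Inclusion criterion 6 (section IV.B) takes adults aged 50 or over with no previous zoster vaccine and places them in one of two cohorts: "Cohort 3 (n=35) will be vaccinated with ZVL at study enrollment", or "Cohort 4 (n=35) will be vaccinated with RZV at study enrollment". The Part B text and schedules in section IV.C give visits, blood draws and challenge timing for each cohort. They do not mention randomisation, an allocation list, concealment or order of enrolment.

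**Eligibility.** Exclusion criterion 3 applies ZVL hypersensitivity to all candidates but "hypersensitivity to RZV or vaccine components in Cohort 4" only.

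**Use of Part B.** Primary Objective 2 compares DNAemia after challenge "at <1y after RZV or ZVL vaccination and at >5y after vaccination". Hypothesis 1 says that RZV "recipients will have a lower rate of varicella-zoster virus (VZV) DNAemia after a live intradermal (ID) VZV challenge" than ZVL recipients, without limiting this to a time since vaccination.

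**Model.** The Data Analysis Plan (section IV.G, kinetics of DNAemia) specifies logistic regression on vaccine group with Wald intervals. Age at vaccination, age at challenge, sex and race are offered as examples of confounders, to be used where suitable. Baseline immunity is not named.

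**Baseline information.** Section III reports that "VZV DNAemia after a vOka skin challenge correlates with the differentiation and magnitude of VZV-CMI responses". Both Part B schedules include a Day 0 blood draw. For Cohort 4 the text puts it before the vaccine: "subjects will be enrolled, have blood (60ml) drawn, and will be administered RZV". For Cohort 3 the order on Day 0 is not explicit.

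**The concern.** Cohorts 3 and 4 draw on the same kind of person, and the study gives both vaccines. It is the only part of the trial where the investigators control which vaccine a participant receives, and so the only place where chance could decide it.

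If the cohorts are filled by preference, convenience or one after the other, they may differ in ways that bear on DNAemia. The protocol gives some reason to expect this. Section II describes RZV as far more efficacious than ZVL (97% against 51%), so people willing to take ZVL may not resemble those who want RZV. Section IV.F expects difficulty in finding never-vaccinated people, which encourages filling whichever cohort is open.

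In Part B, age at vaccination and age at challenge differ only by months, so the four named covariates amount to age, sex and race. Baseline VZV immunity is the obvious further candidate. If it differs between cohorts and predicts DNAemia, the difference will be read as a vaccine effect. The same applies to any comparison of immune responses between Cohorts 3 and 4.

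**Working it through.** **1. The plan's own figure.** Inputs from section IV.G: 86% DNAemia with ZVL, a 2-fold reduction (43%) with RZV, α = 0.05 (taken as two-sided), 80% power.

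n = [1.96·√(2·p̄·q̄) + 0.8416·√(p₁q₁ + p₂q₂)]² / (p₁ − p₂)², with p̄ = 0.645:

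- 1.96·√(2 × 0.645 × 0.355) = 1.326
- 0.8416·√(0.1204 + 0.2451) = 0.509
- (1.835)² / 0.43² = 3.368 / 0.1849 = 18.2, so 19 per group, as stated.

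Power is 81.8% at 19 per group and 97.8% at 35. The issue is bias, not power or arithmetic.

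**2. What the documents cannot give.** They report neither the imbalance between Cohorts 3 and 4 nor the strength of association between pre-vaccination VZV-CMI and DNAemia. Both are assumed below and shown over a range.

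**3. Illustration.** 35 per cohort; no true vaccine effect; overall event rate 56% (the value used in the mediation power calculation); baseline immunity Z normal with SD 1 and cohort means differing by s; logit P(DNAemia) = a − bZ, with a set to give 56% overall. The spurious difference is the gap between the two cohort averages of this probability. Type I error is the simulated rejection rate of the Wald test for vaccine when Z is omitted.

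| b (log-OR per SD) | s (SD) | Rates, Cohort 3 / 4 | Spurious difference (points) | Type I error, Z omitted |
|---|---|---|---|---|
| 0.5 | 0.25 | 57.5% / 54.5% | 2.9 | about 6% |
| 0.5 | 0.50 | 58.9% / 53.1% | 5.8 | about 7% |
| 0.5 | 0.75 | 60.4% / 51.6% | 8.7 | about 10% |
| 1.0 | 0.25 | 58.5% / 53.5% | 5.1 | about 7% |
| 1.0 | 0.50 | 61.1% / 50.9% | 10.2 | about 12% |
| 1.0 | 0.75 | 63.6% / 48.4% | 15.2 | about 24% |

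Differences were taken before the rates were rounded. With Z in the model the error is about 4% to 6% throughout. Simulation error is about 1 point. The table places the higher immunity in Cohort 4; reversing it reverses the sign of the bias.

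**4. Hand check of the extremes** (pooled two-proportion test). Null SE = √(2 × 0.56 × 0.44 / 35) = 0.1187, so the critical difference is 1.96 × 0.1187 = 0.2326.

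- Smallest case: SE under 57.5% vs 54.5% is 0.1186. 1 − Φ((0.2326 − 0.029)/0.1186) + Φ((−0.2326 − 0.029)/0.1186) = 0.043 + 0.014 = 5.7%.
- Largest case: SE under 63.6% vs 48.4% is 0.1173. 1 − Φ((0.2326 − 0.152)/0.1173) + Φ((−0.2326 − 0.152)/0.1173) = 0.246 + 0.001 = 24.7%.

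Both agree with the simulation.

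**5. A cruder version.** Suppose half of participants overall have high baseline immunity and the cohorts differ by 20 points in that share. If DNAemia is 70% with low and 42% with high immunity, the spurious difference is 0.20 × 28 = 5.6 points and type I error is 7.5%. With 86% and 43% it is 0.20 × 43 = 8.6 points and 11.6%.

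**6. What randomisation leaves.** With 35 per group and 50% prevalence, chance imbalance has SD √(2 × 0.25 / 35) = 0.12. The test's α already covers this; systematic selection is not covered.

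**The case against.** Several stronger readings are tempting, and the documents do not support them.

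- *Part B is declared non-randomised.* It is not; the documents are silent. The Cohort 4-only exclusion fits enrolment by cohort, but it is weak evidence, because vaccine-naive people could have known RZV hypersensitivity only through a component.
- *The model is confined to age, sex and race.* The list is open. Baseline VZV-CMI is not pre-specified, but neither is it ruled out. The soluble-factor and phenotype comparisons are also to be adjusted for potential confounders.
- *Unequal visit burden drives selection.* Required clinic visits are 9 in Cohort 3 and 10 in Cohort 4, and blood volumes are 540 and 600 ml. Only the length of participation differs much.
- *Section III shows that pre-vaccination immunity predicts DNAemia.* It reports a correlation with VZV-CMI responses in the setting of a vOka skin challenge. It does not address immunity measured months earlier with a vaccine in between.
- *The <1y RZV versus ZVL contrast is a stated primary test.* Objective 1 concerns >5y only. Objective 2, read with Hypothesis 2, is mainly <1y against >5y within each vaccine. The contrast at <1y is implied, not spelled out.
- *No <1y difference could be attributed to the vaccine.* Attribution is weakened, not made impossible. With a weak association or a small imbalance the type I error barely moves, and age, which section II links to declining VZV-CMI, is a named covariate that may absorb part of the bias.

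These limits stand. They narrow the point without removing it. The plan still names no safeguard against selection in the one place where it could have one, and deciding on the baseline covariate after seeing the data would be a weakness in itself.

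**Conclusion.** The point holds in a limited form. As written, the plan neither states a random allocation for Part B nor pre-specifies adjustment for pre-vaccination VZV-CMI, so the implied <1y RZV versus ZVL contrast carries an avoidable risk of confounding. Its direction and size cannot be known from the documents.

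Under the assumed inputs, the consequence runs from almost nothing (about 3 points, 6% type I error) to serious (about 15 points, 24%). The upper end needs both a log-OR of 1 per SD and a 0.75 SD imbalance, neither of which is documented. The illustration takes no credit for age adjustment.

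A reader might infer that the whole trial's vaccine comparison is affected in a way that randomising Part B would cure. It would not. Part A vaccination is historical, so Objective 1 and the <1y versus >5y contrast stay observational whatever is done here.

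**What to change.** 1. Recruit Cohorts 3 and 4 in parallel under one set of eligibility criteria, and allocate participants not yet enrolled 1:1 from a concealed list.
2. State that the RZV versus ZVL contrast at <1y will be estimated, and pre-specify Day 0 pre-vaccination VZV-CMI as a covariate in that model for all Part B participants.
3. State that the Cohort 3 Day 0 sample is drawn before vaccination.
4. Do not adjust this comparison for VZV-CMI on the day of challenge. Hypotheses 1 and 3 and the mediation analysis treat the vaccine-induced response as the route by which the vaccine acts, so adjusting for it would remove part of the effect.
5. If randomisation is no longer possible, describe how the cohorts were filled, keep steps 2 to 4, and report the contrast as observational.

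**Cost.** A protocol and consent amendment and an allocation list, with no extra participants, samples or visits. The Day 0 samples must be assayed for VZV-CMI if that is not already intended. The real price is recruitment: each participant must accept either vaccine, and section IV.F already expects never-vaccinated people to be hard to find.

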**Exclusion Criteria**

1. Inability or unwillingness of a participant to give written informed consent or to comply with study protocol.
2. Prior history of HZ;
3. Known history of hypersensitivity to ZVL or vaccine components in all study candidates and to hypersensitivity to RZV or vaccine components in Cohort 4.
4. Known neomycin contact allergy or other ZVL components such as gelatin.
5. Untreated anemia in Cohorts 1 and 2.
6. Blood products received in the 3 months prior to study enrollment or planned for the subsequent week for Part A; Part B requires the same exclusion but extends it to the week after the vOka challenge, which is 6 months after completing ZVL or RZV administration.
7. Any confirmed or suspected immunosuppressive or immunodeficient condition resulting from disease (e.g., malignancy, HIV), or immunosuppressive/cytotoxic therapy.
8. Use, or anticipated use, of immunosuppressants or other immune-modifying drugs during the period starting 30 days prior to ID ZVL challenge through 7 days after. This includes chronic administration of corticosteroids (>14 consecutive days of prednisone at a dose of  $\geq$  20 mg/day [or equivalent], long-acting immune-modifying agents, or immunosuppressive/cytotoxic therapy (e.g., medications used during cancer chemotherapy or to treat autoimmune disorders). *Topical, ophthalmic, intra-articular, or inhaled/nebulized steroids are allowed.*
9. Concomitant vaccine received within 2 (inactive) or 4 (live) weeks prior to the study for subjects in all Cohorts, and during the first week of the study. For subjects in Cohorts 3 and 4, no concomitant vaccine received within 2 (inactive) or 4 (live) weeks prior to ID vOka and for the following 7 days.
10. Women of child-bearing potential.
11. Pregnancy or breast-feeding.
12. Participation in a concurrent clinical study in which the subject will be exposed to an investigational product (drug or vaccine) during the period starting 7 days before the first dose of study vaccine through the completion of the study.
13. Antivirals with activity against VZV, including acyclovir, valacyclovir, ganciclovir, valganciclovir, foscarnet, cidofovir, brincidofovir and penciclovir within 7 days of the ID ZVL challenge.
14. Past or current medical problems or findings from physical examination or laboratory testing that are not listed above, which, in the opinion of the investigator, may pose additional risks from participation in the study, may interfere with the participant's ability to comply with study requirements or that may impact the quality or interpretation of the data obtained from the study.

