## C. Study Design and Research Methods

### **Part A; Cohorts 1 and 2**

Seventy subjects with documented evidence of a HZ vaccine at least 5 years previously, divided equally between recipients of ZVL (Cohort 1) or RZV (Cohort 2) - 35 in each group - will be enrolled. Participation will consist of 4 visits over the course of 7-10 days in which blood is drawn, a challenge dose of vOka is given, and a skin biopsy is obtained.

ID vOka challenge live attenuated VZV (as 1 dose of licensed ZVL; Zostavax) will be prepared by mixing 0.35 ml of accompanying diluent with the vaccine and injecting 2 side-by-side intradermal doses of 0.125ml each, for a total of 0.25 ml (about  $\frac{3}{4}$  of the normal dosage or 13,857 plaque forming units) intradermally in the non-dominant deltoid region, using a NanoPass MicronJet600 device, on D0. Blood (60 ml) will be drawn prior to vaccination (D0), and at Days 1, 3, and 7. A skin biopsy (4 mm punch biopsy) will be done at the injection site, on the first 20 subjects (up to 25, if replacements needed) in each vaccine group; five each of these 20 will be biopsied on Day 0, 1, 3, or 7 in the order in which the participants enter the study. The Day 0 biopsy will be done on the contralateral arm in the deltoid region prior to vaccination. Initially every subject enrolled will be required to do the biopsy; this is reflected in the consent. The consent form will be amended to remove references to the biopsy procedure once the number of subjects needed for the biopsies is reached.

Subjects in the ZVL group will be offered RZV vaccine (to comply with ACIP recommendations for shingles immunization), to be administered beginning  $\geq$  60 days after Day 0. If subject wishes to receive the RZV vaccine, 2 additional visits will be required at Day 60 and Day 120, increasing the duration of participation up to 4 months. Subjects will not be reimbursed for these visits but will receive the vaccine free of charge.

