### D. Description, Risks, and Justification of Procedures and Data Collection Tools

#### Risks

Zostavax- The risks are those associated with a licensed vaccine for people 50 years and older. Subjects will be given the relevant Vaccine Information Sheet (VIS).

ID vOka challenge (as 1 dose of licensed ZVL; Zostavax) –The intradermal route was previously studied in ~200 subjects without a noteworthy safety signal (13). The device for ID administration is licensed and was used in a prior study (COMIRB #11-1210). Some subjects will be receiving ZVL for the second time. There is no recommendation for a second dose of ZVL, but we completed a study (COMIRB #10-1461) in which 200 participants safely received a second dose of ZVL. Furthermore, ZVL is recommended after prior herpes zoster, which is analogous to re-exposure (as with our ID challenge) to the virus of herpes zoster. Very rarely, a brief, painless blistery rash limited to the site of injection may develop.

Shingrix – This vaccine will be administered according to the package insert. The risks are those associated with a licensed vaccine for people 50 years and older. Subjects will be given the Vaccine Information Sheet (VIS).

As with all vaccines or drugs, rarely an allergic reaction could occur – a rash, hives or even difficulty breathing.

Risk of receiving multiple shingles vaccines – two doses of RZV have been safely administered to prior ZVL recipients, and also to individuals who had prior HZ. This was done prior to licensure and mentioned in the ACIP recommendation, indicating no concern with an aberrant immune response in this setting.

Blood draws – 60 ml of blood will be taken at each blood draw for a total of 240 ml in 1 week for subjects in Cohorts 1, 2, 3 and 4. Subjects in Cohort 3, receiving ZVL, will have a total of 540 ml drawn over the course of the study. Subjects in Cohort 4, receiving RZV, will have a total of 600 ml drawn, over the course of the study. Neither will have more than 240 ml drawn in a week. The risks of phlebotomy are minimal and include pain, swelling, bruising, or infection around the vein, although this is very uncommon.

Punch biopsy – The skin biopsy will be taken at the ID vOka challenge site (except for Day 0 participants, in which case it will be done on the contralateral arm). The area will be numbed; then a punch biopsy device will be pressed into the skin removing a small circle of skin.

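### The untreated-anemia exclusion covers only Cohorts 1 and 2 (240 ml drawn); Cohorts 3 and 4, with 540 and 600 ml, rely on investigator judgement

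*Combined protocol and SAP*

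**What the plan says.** Section IV.B, Exclusion Criteria, item 5 is "Untreated anemia in Cohorts 1 and 2". The plan does not mention anemia anywhere else. It sets no hemoglobin threshold, and no schedule of events includes a hemoglobin test.

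Two general criteria apply to every cohort. Inclusion item 3 requires participants to be "Ambulatory and in generally good health except for common morbidities of older people". Exclusion item 14 covers medical problems or findings "that are not listed above, which, in the opinion of the investigator, may pose additional risks from participation in the study".

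On blood volume, the Risks part of Section IV.D sets 60 ml per draw, "for a total of 240 ml in 1 week for subjects in Cohorts 1, 2, 3 and 4". It adds: "Subjects in Cohort 3, receiving ZVL, will have a total of 540 ml drawn over the course of the study", and "Subjects in Cohort 4, receiving RZV, will have a total of 600 ml drawn". On harm it says "The risks of phlebotomy are minimal and include pain, swelling, bruising, or infection around the vein"; anemia is not among the risks named.

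Part A alone has a punch biopsy. Section IV.C says "Initially every subject enrolled will be required to do the biopsy; this is reflected in the consent", with the requirement to be dropped once enough biopsies have been taken.

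**The concern.** A reader would expect an anemia exclusion in a study with repeated 60 ml draws to apply at least as firmly where more blood is taken. Here it is named for the two cohorts with the smallest total and omitted for the two with the largest. If item 5 is meant to protect against blood loss, its scope runs opposite to the draw schedule.

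What is at stake is consistent protection of participants. A Part B candidate with known untreated anemia may be enrolled unless the investigator objects, whereas the same person would be barred from Part A. No endpoint, estimate or sample-size figure depends on it.

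**Working it through.** **Inputs.** Draw volume (60 ml) is from Section IV.D, Risks. Draw days are from the schedule-of-events tables in Section IV.C. Total volume is the number of draws × 60 ml. A week means Day d to Day d+7, which is how the plan arrives at its own 240 ml figure.

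**Reproducing the plan's totals.**

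| Cohort | Draw days | Draws × 60 ml | Plan states |
|---|---|---|---|
| 1 and 2 | 0, 1, 3, 7 | 4 × 60 = 240 ml | 240 ml |
| 3 | 0, 1, 3, 7, 30, 150, 151, 153, 157 | 9 × 60 = 540 ml | 540 ml |
| 4 | 0, 60, 61, 63, 67, 90, 240, 241, 243, 247 | 10 × 60 = 600 ml | 600 ml |

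All three agree. The narrative for Cohort 4 omits the Day 60 draw, which would give 9 × 60 = 540 ml. The table marks that draw and the stated 600 ml requires it, so ten draws is the right count.

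**Comparing exposure on nominal days.**

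| | Cohorts 1 and 2 | Cohort 3 | Cohort 4 |
|---|---|---|---|
| Peak 7-day volume | 240 ml | 240 ml | 240 ml |
| Number of 240 ml weeks | 1 (from Day 0) | 2 (from Days 0 and 150) | 2 (from Days 60 and 240) |
| Peak 30-day volume | 240 ml | 300 ml | 300 ml |
| Total | 240 ml | 540 ml | 600 ml |
| Day of last draw | 7 | 157 | 247 |

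**How large the contrast is.**
- Weekly peak: no difference.
- 30-day peak: 300 − 240 = 60 ml, one draw. If the Day 30 visit (Cohort 3) or Day 90 visit (Cohort 4) uses its full +7 window, the 300 ml spans 37 days and the 30-day peak is 240 ml everywhere.
- Gap before the challenge draws, Cohort 3: 150 − 30 = 120 days nominal; with windows, 150 − 37 = 113 to 194 − 30 = 164 days.
- Gap before the challenge draws, Cohort 4: 240 − 90 = 150 days nominal; with windows, 240 − 97 = 143 to 254 − 90 = 164 days.
- Participants without a named criterion: 35 + 35 = 70 of 4 × 35 = 140.

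**Is a reason for the restriction visible?** The biopsy is the only Part A procedure that might explain it. It is a 4 mm punch, done on the first 20 (up to 25) of 35 per vaccine group, and its listed risks do not include anemia. Item 5 covers all 35 per group, and nothing says it lapses when the biopsies are complete. The biopsy is therefore a possible reason but not an evident one.

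**The case against.** The strongest reply is that safeguards already exist and the restriction may be deliberate. Much of this stands.

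- **Existing safeguards.** Inclusion item 3 and exclusion item 14 apply to Cohorts 3 and 4. A reader might infer that item 14 cannot be used for anemia because it is confined to problems not already listed. The text does not support that: item 5 lists anemia for Cohorts 1 and 2 only, so in Cohorts 3 and 4 it is unlisted and item 14 reaches it. What remains is the difference between a named rule and discretion, and inclusion item 3 makes an exception for common morbidities.
- **Blood drawn elsewhere.** A reader might infer that Part B participants give at least as much blood as Part A participants over any interval. That holds only for nominal draws within this protocol. The recruitment paragraph in Section IV.C says the people vaccinated with RZV five years earlier come from a site study that was still sampling them. It gives neither the volume nor the gap before Day 0, so this neither establishes nor excludes a reason for item 5.
- **Scoping by cohort is normal here.** Items 3, 6 and 9 also differ by cohort or Part, so item 5 may be intended. But items 6 and 9 extend coverage for Part B, and item 3 names RZV hypersensitivity for Cohort 4, where RZV is a study vaccine. Item 5 does the reverse without explanation.
- **Small contrast.** Equal weekly peaks and gaps of months between heavy weeks are correct, and they limit the point to a minor one.

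**Conclusion.** The point holds as a minor, inexpensive improvement. Under this protocol the named anemia exclusion is absent from the cohorts with more draws (9 and 10 against 4) and more 240 ml weeks (two against one). No reason is given.

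The conclusion rests on one assumption: that item 5 is at least partly about blood loss. The plan does not say so, and its phlebotomy risks do not name anemia. A reader might go further and infer that anemic participants in Part B are unprotected, or that the restriction is a demonstrated error. The documents support neither: judgement under two general criteria remains available, and intent cannot be read from the text.

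The effect is confined to known untreated anemia. With no hemoglobin test scheduled in any cohort, extending the rule would not detect new cases. Power and the primary analysis are unaffected.

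**What to change.** Delete the cohort restriction, so that item 5 excludes untreated anemia in all four cohorts. Apply it once, at the Day 0 eligibility and medical history review that every schedule already contains. No test or visit is added.

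Do not turn the later medical history reviews (Cohort 3 Day 150; Cohort 4 Days 60 and 240) into further exclusion points. Removing someone after vaccination could cost a DNAemia outcome in a cohort of 35, and asking without a stated consequence would achieve nothing.

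If the restriction is intended, because of the biopsy or for another reason, item 5 should say so instead.

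The cost is a one-line eligibility amendment. A few Part B candidates with known untreated anemia would be ineligible until treated, and Section IV.F already expects vaccine-naive people to be hard to find. The plan gives no anemia prevalence, so that number cannot be estimated. The blood volumes of 240, 540 and 600 ml do not change.
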